### Section 1.2.2 of the CTP

*The Residual Effect Period (REP) of BI 3000202, when measurable drug levels and/or pharmacodynamic effects are still likely to be present, is not known for this first-in-human trial.* [REDACTED]

Based on this, the following study phases will be defined for the analysis of AEs:

- **Screening**
  - Ranging from 0:00 h on day of informed consent until time of first drug administration (BI/Placebo)
- **On-treatment**
  - SRD part: Ranging from the time of drug administration until [REDACTED] after drug administration
  - FE part: Ranging from the time of drug administration until next drug administration OR until [REDACTED] after drug administration, whichever comes first
- **Follow-up (F/U)**
  - SRD part: Ranging from [REDACTED] after drug administration until 0:00 h on the day after trial termination date
  - FE part: Ranging from the end of REP until next drug administration OR until 0:00 h on the day after trial termination date, whichever comes first

### Section 7.2.5 of the CTP

*Note that AEs occurring after the last per protocol contact but entered before unblinding the trial will be reported to Pharmacovigilance only and will not be captured in the trial database.*

The following AE displays will be provided in the report:

AE displays in CTR Section 15.3 and Appendix 16.1.13.1.8 (for ClinicalTrials.gov and EudraCT) will present results for the on-treatment phase (as defined in [Tables 6.1: 1](#) and [6.1: 2](#)) only. Screening and follow-up phase will not be included in this analysis.

The following totals will be provided in addition for Section 15.3:

- a total over all on-treatment phases of the SRD part involving BI drug (“**BI SRD Total**”)
- a total over all on-treatment phases of the SRD part involving BI drug and placebo (“**Total**”)
- a total over all on-treatment phases of the FE part (“**BI FE Total**”)

In Section 15.4 and Appendix 16.2 (Listings) of the CTR displays, the screening period, as well as the follow-up phases will additionally be included and no totals will be provided. The labelling of the actual treatment in listings corresponds to the labelling of study phases defined above. Single exception is the Follow-up phase where the actual treatment will be labelled “F/U”.

More details on the handling of the treatments refer to Technical TSAP ADS (Analysis Data Set) plan and Analysis Data Reviewers guide.

## 6.2 IMPORTANT PROTOCOL DEVIATIONS

Data discrepancies and deviations from the CTP will be identified for all treated subjects. Consistency check listings (for identification of deviations of time windows) and a list of protocol deviations (e.g. deviations in drug administration, in blood sampling times, etc.) will be provided to be discussed at the Report Planning Meeting (RPM). At this meeting, it will be decided whether a discrepant data value can be used in analyses or whether it must be corrected in the clinical database. Each protocol deviation must be assessed to determine whether it is an important protocol deviation (iPD).

For definition of important protocol deviations (iPD), and for the process of identification of these, refer to the Boehringer Ingelheim (BI) Standard Operating Procedure (SOP) “Identify and Manage Important Protocol Deviations (iPD)” ([2](#)).

iPD categories will be suggested in the DV domain sheet, iPDs will be identified no later than in the Report Planning Meeting, and the iPD categories will be updated as needed.

If any iPDs are identified, they are to be summarised into categories and will be captured in the iPD specification file (DV domain) ([3](#)) and in the decision log ([4](#)). Both documents will be stored within the trial master file (TMF) in electronic document management system (EDMS).

The iPDs will be summarized and listed in the CTR. Non-important COVID-19 related protocol deviations will only be listed.

### 6.3 INTERCURRENT EVENTS

This section is not applicable.

### 6.4 SUBJECT SETS ANALYSED

The treated set (TS), the pharmacokinetic parameter analysis set (PKS) and the pharmacodynamic parameter analysis set (PDS) will be used as defined in the CTP, Section 7.2.1.1:

*Statistical analyses will be based on the following analysis sets:*

- *Treated set (TS): The treated set includes all subjects who were treated with at least one dose of trial drug. The treatment assignment will be determined based on the first treatment the subjects received. The treated set will be used for safety analyses.*
- *Pharmacokinetic parameter analysis set (PKS): This set includes all subjects in the treated set (TS) who provide at least one PK endpoint that was not excluded due to a protocol deviation relevant to the evaluation of PK or due to PK non-evaluability (as specified in the following CTP subsection 'Pharmacokinetics'). Thus, a subject will be included in the PKS, even if he/she contributes only one PK parameter value for one period to the statistical assessment. Descriptive and model-based analyses of PK parameters will be based on the PKS.*

*For the SRD part, the following analysis set will be created in addition:*

- *Pharmacodynamic parameter analysis set (PDS): This set includes all subjects in the treated set (TS) who provide at least one PD endpoint (see CTP Section 2.2.2.3) that was not excluded due to a protocol deviation relevant to the evaluation of PD or due to PD non-evaluability (as specified in the CTP subsection 7.2.1.3 'Biomarkers'). Descriptive analyses of PD endpoints will be based on the PDS.*

All ECG analyses are performed on the TS, [REDACTED]

[REDACTED]

[REDACTED]

Table 6.4: 1 Subject sets analysed

Class of analysis	TS	Subject set		
		PKS	PDS	
Primary endpoint (SRD part)	X			
Primary and secondary PK endpoints		X		
Further PK endpoints		X		
Biomarker/PD endpoints			X	
Safety & treatment exposure	X			
iPDs	X			
Disposition	X			
Demographic & baseline	X			

## 6.6 HANDLING OF MISSING DATA AND OUTLIERS

### Section 3.3.4 of the CTP:

*If a subject is removed from or withdraws from the trial prior to the first administration of trial medication, the data of this subject will not be entered in the case report form (CRF) and will not be reported in the clinical trial report (CTR).*

*If a subject is removed from or withdraws from the trial after the first administration of trial medication, this will be documented and the reason for discontinuation must be recorded in the CRF; in addition, trial data will be included in the CRF and will be reported in the CTR.*

### Section 7.3.1 of the CTP:

*It is not planned to impute missing values for safety parameters.*

Missing or incomplete AE dates are imputed according to BI standards (5).

### Section 7.3.2 and 7.3.3 of the CTP:

*Handling of missing PK data will be performed according to the relevant BI internal procedure.*

*PK parameters that cannot be reasonably calculated based on the available drug concentration-time data will not be imputed.*

Missing data and outliers of PK and PD data are handled according to BI standards (6) and (7).

[REDACTED]

No imputation will be done for ECG endpoints. If replicate ECG recordings are missing, the arithmetic means per time point will be computed with the reduced (1 or 2) number of recordings. If single cardiac cycles (also denoted as beats or waveforms) are missing, the arithmetic mean per single ECG will be computed with the reduced (1, 2 or 3) number of cardiac cycles.

## 6.7 BASELINE, TIME WINDOWS AND CALCULATED VISITS

[REDACTED]

For all analyses (except for analyses of ECG variables), the baseline value is defined as the last measurement prior to the drug administration (in each treatment period for FE part).

There will be a centralised evaluation of the 12-lead ECG recordings at the time points and for the ECG recordings specified in [Table 6.7: 1](#) below. This will be performed for the SRD part only.

Three triplicate ECGs will be recorded as the baseline before the first drug administration, but only the first ECG of each of the 3 baseline triplicates will be transferred to the database. At all other time points, 1 triplicate ECG will be recorded, but only the first single ECG of the triplicate will be transferred to the database. The baseline value of an ECG variable is defined as the mean of the ECG variable values prior to drug administration.

[REDACTED]

Unscheduled measurements of laboratory data and vital signs data will be assumed to be repeat measurements of the most recent scheduled measurement (e.g. for follow-up or

confirmation of a particular value). Therefore, unscheduled measurements will be assigned to the planned time point of the previous scheduled measurement.

Table 6.7: 1 Time schedule of 12-lead ECG recordings

Visit	Day	Planned time (hh:mm) (relative to drug administration)	Study phase	Central evaluation
1	-21 to -1		Screening	NA
2	1	-01:00	Baseline	first ECG of each of the 3 triplicate baselines
		-00:45		
		-00:30		
		00:30	On-treatment	first single ECG of the triplicate
		01:00		
		01:30		
		02:00		
		03:00		
		04:00		
		06:00		
		08:00		
		12:00		
	2	24:00		
	3	48:00		NA
4	4 to 14		End-of-study examination	NA

Time windows are defined in Section 6.1 of the CTP. Adherence to time windows will be checked at the RPM.

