Visit	Day	Planned time (relative to drug administration) (h:min)	Approximate clock time of actual day (h:min)	Event and comment	Safety laboratory ⁸	PK blood ^{10,12}	PK urine ^{10,13}	PD blood ¹⁰	12-lead ECG ⁹	Continuous ECG monitoring	Vital signs (BP, PR)	Questioning for AEs and concomitant therapy ⁶
1	-21 to -1			Screening (SCR) ¹	x ^A				x		x	
2	-3 to -1	-74:00 ⁷	06:00	Ambulatory visit	x ^{B,7}							x
	1	-1:30	06:30	Admission to trial site ²								
		-1:00	07:00		x ⁵				x ^{2,9}	x ²	x ²	x ²
		-0:45	07:15						x ^{2,9}			
		-0:30	07:30	Allocation to treatment ²	x ^{C,2}	x ²	x ²	x ²	x ^{2,9}			
		0:00	08:00	Drug administration			▲			▲		
		0:15	08:15			x						
		0:30	08:30			x			x ⁹		x	x
		0:45	08:45			x						
		1:00	09:00			x		x	x ⁹		x	x
		1:30	09:30			x ¹¹			x ⁹			
		2:00	10:00	240 mL fluid intake		x		x	x ⁹		x	x
		2:30	10:30			x						
		3:00	11:00			x			x ⁹		x	x
		4:00	12:00	240 mL fluid intake, thereafter lunch ³		x	+	x	x ⁹	▼	x	x
		5:00	13:00			x						
		6:00	14:00			x		x	x ⁹			
		7:00	15:00	Snack (voluntary) ³								
		8:00	16:00			x	+	x	x ⁹		x	x
		10:00	18:00	Dinner ³								
		12:00	20:00			x	+		x ⁹		x	x
	2	24:00	08:00	Breakfast (voluntary) ³ , discharge from trial site	x ^C	x	▼	x	x ⁹		x	x
	3	48:00	08:00	Ambulatory visit		x		x ¹⁴	x ⁹		x	x
4	4 to 14			End of study (EoS) examination ⁴	x ^D				x		x	x

- Subject must be informed and written informed consent obtained prior to starting any screening procedures. Screening procedures include physical examination, check of vital signs, 12-lead ECG and rhythm strip over at least 15 min, safety laboratory (including drug screening and infectious serology), demographics (including determination of body height and weight, smoking status and alcohol history), medical history, concomitant therapy and review of inclusion/exclusion criteria. Pharmacogenetic samples will be collected if needed.
- The time is approximate; procedures are to be performed and completed within the 3 h prior to drug administration. Allocation to treatment may be performed at any time following enrolment but must be completed prior to drug administration.
- If several actions are indicated at the same time, the intake of meals will be the last action..
- At the end of study (synonym for End of Trial), the EoS examination includes physical examination, vital signs, ECG, safety laboratory, recording of AEs, and concomitant therapies.
- Urine drug screening and alcohol breath test only

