Bruising and, in rare cases, phlebitis, or nerve injury, potentially resulting in paraesthesia, reduced sensibility, and/or pain	General risk by venipuncture for blood sampling, acceptable in the framework of trial participation.	Medical expertise of the trial site

In addition, the following general safety measures will be applied in order to minimize the risk to the healthy volunteers:

- Dose selection is based on the expected pharmacologically active dose, expected systemic exposures after single-dose administration, and toxicity findings in preclinical studies. Escalation factors between dose steps decrease at higher doses. For details see Sections [1.3.1](#), [1.3.2](#), and [1.3.3](#).
- A maximum acceptable human exposure has been defined based on toxicity findings (see Section 1.3.3). Dose escalation is guided by preliminary analysis of BI 3000202 PK (C_{\max} and AUC_{0-24}).
 - A dose level will only be administered if estimated (predicted) gMean values for C_{\max} and AUC_{0-24} do not exceed the maximum acceptable human exposure (see Section 1.3.3 and Section [3.3.4.3](#)).
 - Moreover, dose escalation will be stopped in case observed exposure in one subject who has been dosed with BI 3000202 has exceeded the maximum acceptable exposure (see Section 3.3.4.3)
- A documented Safety Review takes place prior to each dose escalation (for details, refer to Section [3.1](#))
- For safety reasons, each dose group of 8 subjects (6 on active and 2 on placebo) will be divided into two cohorts of 2 subjects each (1st and 2nd cohort) and one cohort of 4 subjects (3rd cohort). Further details are provided in Section 3.1.
- Stringent in- and exclusion criteria define a relatively homogenous population and exclude subjects that might be at increased risk for adverse events (see Section [3.3](#)).
- Safety laboratory examinations will be performed at pre-defined time points (see [Flow Chart - SRD Part](#) and [Flow Chart – FE Part](#)) before and 24 hours after drug administration. These examinations include extensive standard safety laboratory examinations (see Section [5.2.3](#)).

- A thorough ECG and heart rate monitoring including continuous ECG monitoring in the SRD part for 4 h post dose and in addition frequent 12-lead ECG and vital signs measurements at time points as described in the [Flow Charts for SRD](#) and [FE part](#) are planned.

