	Potassium	X	--	X	X
	Calcium	X	--	X	X

A: parameters to be determined at the screening examination

B: parameters to be determined at Visit 2 on Days -3, -2 or -1 (laboratory assessment can be omitted if screening examination is performed on Days -3, -2 or -1), for time point refer to [Flow Chart – SRD Part](#) and [Flow Chart – FE Part](#)

C: parameters to be determined on Day 1 (predose) and Day 2 of each treatment period (see Flow Chart - SRD Part and Flow Chart – FE Part)

D: parameters to be determined at the end of trial examination

Table 5.2.3: 1 Routine laboratory tests (cont.)

Functional lab group	BI test name (comment/abbreviation)	A	B	C	D
Urinalysis (Stix)	Urine Nitrite (qual)	X	--	X	X
	Urine Protein (qual)	X	--	X	X
	Urine Glucose (qual)	X	--	X	X
	Urine Ketone (qual)	X	--	X	X
	Urobilinogen (qual)	X	--	X	X
	Urine Bilirubin (qual)	X	--	X	X
	Urine HGB (qual)	X	--	X	X
	Urine Leucocyte esterase (qual)	X	--	X	X
	Urine pH	X	--	X	X
Urine sediment (microscopic examination if erythrocytes, leukocytes nitrite or protein are abnormal in urine)	Only positive findings will be reported (for instance, the presence of sediment bacteria, casts in sediment, squamous epithelial cells, erythrocytes, leukocytes)				

A: parameters to be determined at the screening examination

B: parameters to be determined at Visit 2 on Days -3, -2 or -1 (laboratory assessment can be omitted if screening examination is performed on Days -3, -2 or -1), for time point refer to [Flow Chart – SRD Part](#) and [Flow Chart – FE Part](#))

C: parameters to be determined on Day 1 (predose) and Day 2 of each treatment period (see Flow Chart - SRD Part and Flow Chart – FE Part)

D: parameters to be determined at the end of trial examination

The tests listed in Table [5.2.3: 2](#) are exclusionary laboratory tests that may be repeated as required. The results will not be entered in the CRF/database and will not be reported in the CTR. Except for drug screening, it is planned to perform these tests at screening only. Drug screening will be performed at screening and prior to drug administration(s).

Table 5.2.3: 2 Exclusionary laboratory tests

Functional lab group	Test name
Drug screening (urine)	Amphetamine/MDA
	Barbiturates
	Benzodiazepine
	Cannabis
	Cocaine
	Methadone
	Methamphetamines/MDMA/Ecstasy
	Opiates
	Phencyclidine
	Tricyclic antidepressants
Infectious serology (blood)	Hepatitis A antibodies (qualitative)
	Hepatitis B surface antigen (qualitative)

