7.2.5 Safety analyses

Safety will be assessed as defined by the endpoints listed in Section [2.1.2](#) and [2.2.2](#) based on the treated set (TS). Safety analyses will be descriptive in nature and will be based on BI standards.

For all analyses the treatment actually administered (= treatment at onset) to the subject will be used (any deviations from the randomised treatment will be discussed in the minutes of the Report Planning Meeting).

Treatments will be compared in a descriptive way. The placebo group in the safety evaluation will consist of all subjects treated with placebo, regardless of the dose group in which they were treated. The test treatment groups will be compared to the placebo group in a descriptive way. Tabulations of frequencies/proportions will be used for the evaluation of categorical (qualitative) data, and tabulations of descriptive statistics will be used to analyse continuous (quantitative) data.

Measurements (such as ECGs, vital signs, or laboratory parameters) or AEs will be assigned to treatments (see Section [4.1](#)) based on the actual treatment at the time of the measurement or on the recorded time of AE onset (concept of treatment-emergent AEs). Therefore, measurements performed or AEs recorded prior to intake of trial medication will be assigned to the screening period, those between the trial medication intake and end of REP (see Section [1.2.2](#)) will be assigned to the treatment period. Events occurring after the REP but prior to trial termination date will be assigned to 'follow-up'. These assignments including the corresponding time intervals will be defined in detail in the TSAP. Note that AEs occurring after the last per protocol contact but entered before unblinding the trial will be reported to Pharmacovigilance only and will not be captured in the trial database.

Additionally, further treatment intervals (called analysing treatments) may be defined in the TSAP in order to provide summary statistics for other than above periods, such as combined

treatments, on-treatment totals, or periods without treatment effects (such as screening and post-study intervals).

Adverse events will be coded using the Medical Dictionary for Regulatory Activities (MedDRA). Frequency, severity, and causal relationship of AEs will be tabulated by treatment, system organ class and preferred term. SAEs, AESIs (see Section 5.2.6.1) and other significant AEs (according to ICH E3) will be listed separately.

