## 7.8.2 Laboratory data

The analyses of laboratory data will be descriptive in nature and will be based on BI standards “Handling, Display and Analysis of Laboratory Data” (14). Analyses will be based on normalised values, which means transforming to a standard unit and a standard reference range. The original values will be analysed if the transformation into standard unit is not possible for a parameter.

Laboratory data will be analysed qualitatively via comparison of laboratory data to their reference ranges. Values outside the reference range will be flagged in the data listings.

Clinically relevant findings in laboratory data will be reported as baseline conditions (at screening) or as AEs (during the trial) if judged clinically relevant by the investigator, and will be analysed as such (checked at the RPM at the latest).

Descriptive statistics of laboratory data including change from baseline will be calculated by planned time point based on the worst value of the subject at that planned time point (or assigned to that planned time point).

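### SAP 6.7 has no visible exception for an intervening dose, so unscheduled laboratory values from 0 to 24 h after dosing, and vital signs before the first post-dose reading, are tabulated as pre-dose

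*SAP*

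**What the plan says.** SAP 6.7 sets the rule and its rationale. "Unscheduled measurements of laboratory data and vital signs data will be assumed to be repeat measurements of the most recent scheduled measurement", for instance to follow up or confirm a value. The consequence follows: "Therefore, unscheduled measurements will be assigned to the planned time point of the previous scheduled measurement". The same section defines baseline for everything except ECG variables: "the baseline value is defined as the last measurement prior to the drug administration (in each treatment period for FE part").

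SAP 7.8.2 builds the laboratory summaries, including change from baseline, by planned time point, "based on the worst value of the subject at that planned time point (or assigned to that planned time point"). SAP 7.8.3, on vital signs, states no worst-value rule.

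Protocol 5.2.3 fixes the laboratory schedule around dosing: "C: parameters to be determined on Day 1 (predose) and Day 2 of each treatment period". Protocol 1.4.2 confirms that these tests are done "before and 24 hours after drug administration".

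Protocol 7.2.5 assigns measurements, naming vital signs and laboratory parameters, "based on the actual treatment at the time of the measurement or on the recorded time of AE onset". Measurements before intake belong to screening, and those from intake to the end of the residual effect period (REP) belong to the treatment period. The detailed intervals are left to the SAP. SAP 6.1 defines phases for the analysis of AEs only. SAP 4 states that all analyses accord with the revised protocol.

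**The concern.** Carrying an unscheduled value back to the last scheduled time is harmless when both lie on the same side of the dose. It goes wrong when the dose lies between them, because a value measured on drug then sits in a row that readers take as untreated. The laboratory schedule has no time point between pre-dose and 24:00, so this applies to every unscheduled laboratory sample in the first day.

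Not all such samples are repeats. Protocol 5.2.6.1.4 foresees an unscheduled blood test when symptoms of hepatic injury appear. Protocol 1.4.2 names laboratory testing as the mitigation for bilirubin increase, lymphocyte changes and liver injury. An abnormal early value is thus the one most likely to be placed in the wrong row. The worst-value rule makes it the value reported there.

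**Working it through.** The plan gives no figure to reproduce. The check applies the SAP rule to the schedules in the two protocol flow charts.

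**Inputs.** Laboratory: SRD -0:30 and 24:00; FE -1:00 and 24:00 in each period. Vital signs: SRD -1:00, 0:30, 1:00, 2:00, 3:00, 4:00, 8:00, 12:00, 24:00 and 48:00; FE -1:00, 1:30, 4:00 and 24:00.

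**Rule.** Assigned time = latest scheduled time at or before the actual time. A post-dose value is assigned to pre-dose if it is taken before the first scheduled post-dose time.

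| Data | Part | Assigned pre-dose time | First post-dose time | Affected window | Share of first 24 h |
|---|---|---|---|---|---|
| Laboratory | SRD | -0:30 | 24:00 | 0 to 24 h | 24/24 = 100% |
| Laboratory | FE, each period | -1:00 | 24:00 | 0 to 24 h | 24/24 = 100% |
| Vital signs | SRD | -1:00 | 0:30 | 0 to 0.5 h | 0.5/24 = 2.1% |
| Vital signs | FE, each period | -1:00 | 1:30 | 0 to 1.5 h | 1.5/24 = 6.25% |

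For example, an unscheduled value at 6 h goes to pre-dose for laboratory data but to 4:00 for vital signs in both parts. At 18 h, vital signs go to 12:00 (SRD) or 4:00 (FE), both post-dose.

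**Effect on a laboratory mean (assumed values).** Suppose one subject's unscheduled value exceeds his pre-dose value by d, and the table column has n subjects. The pre-dose mean shifts by d/n.

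- Assume creatine kinase is 150 in six active subjects and one has an unscheduled 6-h value of 900. The pre-dose mean becomes (5 × 150 + 900)/6 = 275 instead of 150, a shift of 750/6 = 125.
- With d = 750, pooled placebo (n = 7 × 2 = 14) shifts by 750/14 = 53.6, and an FE treatment (n = 12) by 750/12 = 62.5.
- With a smaller assumed excess, d = 150, the shifts are 25 (n = 6), 10.7 (n = 14) and 12.5 (n = 12).

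**Effect on baseline.** There are two readings.

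- If actual time selects the baseline, it stays 150. The pre-dose row then shows a change from baseline of 900 - 150 = +750 for that subject, although the sample was taken on drug. Later changes are unaffected.
- If planned time selects it, the 6-h value could become the baseline, and that subject's later changes would be understated by 750.

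The wording of SAP 6.7 favours the first reading but does not say which time governs.

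**After the fix.** If actual time relative to dosing decides, all four windows shrink to 0 h.

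**The case against.** The strongest reply is that the two documents govern different things. Protocol 7.2.5 assigns measurements to treatments and study periods, whereas SAP 6.7 assigns a planned-time label and does not say that a value changes phase. The protocol also leaves the intervals to the SAP. This stands in part: there is no word-for-word contradiction. But the label in question lies before intake, which the protocol places in screening, and the visible SAP gives no other phase rule for laboratory data. The length of the REP is not visible, but a value taken after intake is never a screening value.

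Several stronger readings are tempting, and the documents do not support them:

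- **A reader might infer that vital signs are affected throughout the first 24 h.** The flow charts limit this to the time before the first post-dose reading.
- **A reader might infer that baseline is corrupted.** On its plain wording, baseline precedes dosing.
- **A reader might infer that the safety signal is lost.** All individual values are listed, out-of-range laboratory values are flagged, and clinically relevant findings become AEs, which are assigned by onset. The SRD primary endpoint counts drug-related AEs. Escalation rests on documented safety reviews during the trial. None of these uses the by-time-point tables.
- **A reader might object to the worst-value rule itself,** since the worse of two independent, equally distributed values lies on average 0.56 SD beyond a single one. That applies only to a subject with a repeat (about 0.56/6 = 0.09 SD in a mean of six). Worst-value reporting is also a defensible, conservative choice, so replacing it is a preference.

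Two further replies stand. The missing row between pre-dose and 24:00 comes from the schedule, so a corrected rule needs somewhere to put these values. Parts of SAP 6.7 are redacted, and laboratory handling also follows a sponsor standard that is not available here, so an exception for dosing cannot be excluded.

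**Conclusion.** The point holds in a limited form and is minor. On the visible text, the SAP rule puts post-dose values at a pre-dose time point for 100% of the first 24 h for laboratory data (both parts, each FE period), and for the first 0.5 h (SRD) or 1.5 h (FE) for vital signs. For laboratory data, the worst-value rule lets such a value displace the true pre-dose value in the summary. This is inconsistent with Protocol 7.2.5 and with the statement of accordance in SAP 4.

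The harm is confined to descriptive by-time-point tables and depends on how many unscheduled samples are taken, which the documents cannot tell us. With six active subjects per dose group, a single one can visibly move a mean. The conclusion assumes that no redacted text or cited standard already excludes assignment across a dose, and that the flow-chart times are not changed during the trial.

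**What to change.** In SAP 6.7, state that:

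- an unscheduled value taken after dosing is never assigned to a pre-dose time point, and its study phase follows its actual time;
- baseline is selected by actual time relative to dosing, in each FE period.

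In SAP 7.8.2 and 7.8.3, state where such values are summarised: in a separate row for unscheduled on-treatment values, or at a post-dose planned time. The worst-value summary can stay. If an exception for dosing already exists in a sponsor standard, a cross-reference to it is enough.

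The cost is a few sentences of SAP text and minor programming, with no new data and no change to trial conduct.

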5.2.6.1.4 Adverse events of special interest

The term adverse events of special interest (AESI) relates to any specific AE that has been identified at the project level as being of particular concern for prospective safety monitoring and safety assessment within this trial, e.g. the potential for AEs based on knowledge from other compounds in the same class. AESIs need to be reported to the sponsor’s Pharmacovigilance Department within the same timeframe that applies to SAEs, please see Section [5.2.6.2.2](#).

The following are considered as AESIs:

- Potential severe DILI
A potential severe Drug Induced Liver Injury (DILI) that requires follow-up is defined by the following alterations of hepatic laboratory parameters:
 - o An elevation of AST (aspartate aminotransferase) and/or ALT (alanine aminotransferase) ≥ 3 -fold ULN combined with an elevation of total bilirubin ≥ 2 -fold ULN measured in the same blood sample, or in samples drawn within 30 days of each other, or
 - o Aminotransferase (ALT, and/or AST) elevations ≥ 10 -fold ULN

These lab findings constitute a hepatic injury alert and the subjects showing these lab abnormalities need to be followed up according to the ‘DILI checklist’ provided in the

ISF. In case of clinical symptoms of hepatic injury (icterus, unexplained encephalopathy, unexplained coagulopathy, right upper quadrant abdominal pain, etc.) without lab results (ALT, AST, total bilirubin) available, the Investigator should make sure that these parameters are analysed, if necessary, in an unscheduled blood test. Should the results meet the criteria of hepatic injury alert, the procedures described in the DILI checklist should be followed.

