### 7.8.3 Vital signs

The analyses of vital signs (blood pressure, pulse rate) will be descriptive in nature. Descriptive statistics of vital signs over time and for the difference from baseline (see [Section 6.7](#)) will be provided. In addition, the time profiles of median and (min, max) will be displayed graphically by treatment.

Clinically relevant findings in vital signs data will be reported as baseline conditions (prior to first administration of study treatment) or as AEs (after first administration of study treatment) if judged clinically relevant by the investigator, and will be analysed as such.

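### SAP 6.7 lets an unscheduled laboratory value taken after dosing be tabulated as pre-dose, so a transient early abnormality can be missing from every post-dose row

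*SAP*

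**What the plan says.** SAP 6.7 presumes that unscheduled laboratory and vital-sign values "will be assumed to be repeat measurements of the most recent scheduled measurement", giving follow-up or confirmation of a value as examples. It concludes that "unscheduled measurements will be assigned to the planned time point of the previous scheduled measurement". The visible text does not say what happens if the subject was dosed between the two.

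SAP 7.8.2 tabulates laboratory data, including change from baseline, by planned time point, "based on the worst value of the subject at that planned time point (or assigned to that planned time point". SAP 7.8.3 plans "Descriptive statistics of vital signs over time and for the difference from baseline" but gives no rule for several vital-sign values at one time point.

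For all variables except ECG, SAP 6.7 says that "the baseline value is defined as the last measurement prior to the drug administration".

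Protocol 7.2.5 assigns measurements, naming laboratory parameters and vital signs, "based on the actual treatment at the time of the measurement". It places those between intake and the end of the residual effect period in the treatment period and leaves the details to the SAP. SAP 6.1 then defines study phases for adverse events only. SAP Section 4 declares the analyses to be in accordance with the protocol.

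**The concern.** The rule suits a true repeat, such as a second tube drawn because the first result was doubtful. It does not suit a sample drawn because something happened after dosing. Such a value would be shown as a pre-dose finding.

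Unscheduled sampling is foreseen. If symptoms suggest hepatic injury and no results are at hand, Protocol 5.2.6.1.4 asks the investigator to make sure that "these parameters are analysed, if necessary, in an unscheduled blood test". Protocol 5.2.3 allows retests at the investigator's discretion. Protocol Table 1.4.2: 1 relies on laboratory testing to follow bilirubin and lymphocyte counts.

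At stake is whether the by-time-point laboratory tables of a first-in-human trial show a short-lived post-dose abnormality on the correct side of the dose.

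**Working it through.** The plan gives no figure to reproduce. The check applies the SAP rule to the schedule.

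**Scheduled times** (both flow charts; Protocol Table 5.2.3: 1 describes laboratory set C as "parameters to be determined on Day 1 (predose) and Day 2 of each treatment period"):

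| Data | Last pre-dose | First post-dose | Post-dose window labelled pre-dose | Share of the 24-h stay |
|---|---|---|---|---|
| Laboratory, SRD | -0:30 | 24:00 | 0 to 24 h | 24/24 = 100% |
| Laboratory, FE | -1:00 | 24:00 | 0 to 24 h | 24/24 = 100% |
| Vital signs, SRD | -1:00 | 0:30 | 0 to 0.5 h | 0.5/24 = 2.1% |
| Vital signs, FE | -1:00 | 1:30 | 0 to 1.5 h | 1.5/24 = 6.25% |

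**Rule.** Assigned time = latest scheduled time not after the actual time. A laboratory sample at 6 h goes to -0:30 (SRD) or -1:00 (FE). A vital-sign reading at 6 h goes to the 4:00 point in either part and is correctly post-dose.

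**Illustration (all values assumed, arbitrary units).** Bilirubin in six subjects on active drug:

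- Pre-dose: 10, 11, 12, 12, 13, 14; sum 72, mean 72/6 = 12.0.
- 24 h: 10, 12, 12, 13, 13, 15; sum 75, mean 75/6 = 12.5.
- Subject 6 also has an unscheduled value of 40 at 6 h.

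Under the SAP as written:

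- Pre-dose row: (72 - 14 + 40)/6 = 98/6 = 16.33.
- 24-h row: 12.50. Change from baseline: 12.50 - 12.00 = +0.50.
- The value 40 is in no post-dose row.

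If the 6-h value were counted as post-dose (here in a worst on-treatment row):

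- Pre-dose row: 12.00.
- Worst on-treatment row: (75 - 15 + 40)/6 = 100/6 = 16.67. Change from baseline: +4.67.

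Baseline for subject 6 is 14 under either rule, because it is the last value before dosing. The tabulated pre-dose mean therefore lies 16.33 - 12.00 = 4.33 above the mean baseline.

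**Against the protocol.** A sample taken after intake cannot belong to the screening period under Protocol 7.2.5. It belongs to the treatment period, or to follow-up if the residual effect period has ended. A row labelled pre-dose fits neither.

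**The case against.** The strongest reply is that little depends on these tables. SAP Section 7 lists all individual values, and SAP 7.8.2 flags those outside the reference range. Findings judged clinically relevant become adverse events. Under SAP 6.1, these are assigned to phases that start at the actual time of dosing. A hepatic injury alert is an adverse event of special interest with its own table. The SRD primary endpoint counts drug-related adverse events, and escalation reviews use the available safety data, not the report's tables. All of this stands, and it limits the point to the by-time-point summaries.

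Second, Protocol 7.2.5 assigns values to treatments and periods, whereas SAP 6.7 assigns a planned time for display. No value moves to another treatment column. That also stands, but a pre-dose row is read as the state before treatment, and the SAP does not supply the phase assignment for these data that the protocol leaves to it.

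Third, parts of SAP 6.7 are blacked out, and the sponsor's laboratory standard is not available, so an exception may exist there. This cannot be excluded, but the visible sentence is explicit and has none.

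Fourth, a post-dose retest of an abnormal pre-dose result is a genuine repeat, and moving it after the dose has a cost. This is correct and is reflected in the fix.

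A reader might go further and infer that an acute drug effect is hidden, or that the change from baseline turns negative (12.50 - 16.33 = -3.83 in the illustration). The documents do not support this. Change is taken from the last value before dosing, so -3.83 is not an SAP output, and a pre-dose row 4.33 above baseline is a visible anomaly. Nor do all early abnormalities drop out: those still present at the next scheduled check appear post-dose.

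**Conclusion.** The point holds for the by-time-point laboratory summaries in both parts. Any unscheduled laboratory value from the first 24 h after dosing carries a pre-dose label. If it is worse than the scheduled pre-dose value, it replaces it in that row. If the abnormality has resolved by 24 h, no post-dose row shows it. For vital signs only the mislabelling holds, within 30 or 90 min of dosing; replacement of the pre-dose value cannot be asserted, because the worst-value rule is stated for laboratory data only.

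Baseline, change from baseline at scheduled post-dose points, listings, adverse event tables, the primary endpoint and escalation reviews are unaffected, provided that baseline is derived from actual times. The documents do not say how many unscheduled samples to expect, and there may be none. The numerical example shows the mechanism, not a likely size. The conclusion also assumes that no blacked-out text or sponsor standard already contains an exception. The change is worth making because a stated rule gives a wrong tabulation and the correction is small.

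**What to change.** Amend SAP 6.7 to say: an unscheduled laboratory or vital-sign value is assigned to the previous scheduled time point only if both lie on the same side of the actual dosing time; a value taken after dosing is never assigned to a pre-dose time point. Where no scheduled post-dose measurement has yet been made in that period, show the value in a separate 'unscheduled post-dose' or 'worst on-treatment' row. The sponsor could instead place it at the first scheduled post-dose point with a footnote, but a 6-h value labelled 24:00 is itself imprecise. If an exception already exists in a sponsor standard, a cross-reference in SAP 6.7 would do.

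The cost is one sentence, one condition in the derivation program and one extra table row, with no new data. The downside is that a post-dose retest of an abnormal pre-dose value will be shown as on-treatment. It can be read against the subject's baseline, which is unchanged.
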